6.1.5 Other Treatment Procedures

There are no other treatment procedures in this study.

6.1.6 Product Complaints

A product complaint is any written, electronic or oral communication that alleges deficiencies related to the identity, quality, durability, reliability, safety, effectiveness, or performance of a drug(s) or device(s) after it is released for distribution to market or clinic by either Amgen or by distributors and partners for whom Amgen manufactures the material.

This includes any investigational product(s) provisioned and/or repackaged/modified by Amgen (ie, AMG 910).

Any product complaint(s) associated with an investigational product(s) supplied by Amgen are to be reported according to the instructions provided in the IPIM.

6.1.7 Excluded Treatments, Medical Devices, and/or Procedures During Study Period

The following treatments and/or procedures are excluded during the treatment period of the study (until safety follow-up):

- Any antitumor therapy other than AMG 910, such as:
 - Cytotoxic and/or cytostatic drugs
 - Radiation therapy (with the exception of radiotherapy for palliative care such as bone pain; this is only permitted after discussion with Amgen Medical Monitor)
 - Immunotherapy
- Exception: recommended preventive vaccinations may be administered in the treatment-free intervals (such as anti-flu or other anti-infective vaccinations); **however, such vaccinations should not be given during the DLT period of an individual subject.**

- Chronic systemic corticosteroid therapy or any other immunosuppressive therapies (except for the management of acute, treatment related toxicities such as transient [ie, for up to 2 weeks] use of corticosteroids and tocilizumab). Recent or current use of inhaled steroids or physiological substitution in case of adrenal insufficiency is not exclusionary.
- Long-term antiplatelet treatment (aspirin, dosage > 300 mg/d; clopidogrel, dosage > 75 mg/d)
- Any other investigational agent
- Any major surgery

6.2 Dose Modification

6.2.1 Dose-cohort Study Escalation/De-escalation and Stopping Rules

6.2.1.1 Dose-exploration Phase

The dose-exploration phase of the study will enroll up to 34 subjects with gastric cancer.

[Table 6-2](#) describes the planned dose levels for investigation. Dose exploration will be conducted in 2 stages: single-subject cohort(s) followed by multiple-subject cohort(s) (3 to 4 subjects per cohort).

Table 6-2. Planned AMG 910 Target Doses per Dose Cohort Level

Cohort number	Number of subjects ^a	Dose (µg) Route
(-1)	(3 to 4)	2.5 IV
1	3 to 4	6.5 ^b eIV
1b	3 to 4	6.5 ^b eIV
2b	3 to 4	15 eIV
3b	3 to 4	30 eIV
4b	3 to 4	60 eIV
5b	3 to 4	150 eIV
6b	3 to 4	300 eIV
7b	3 to 4	600 eIV
8b	3 to 4	1000 eIV
9b	3 to 4	2000 eIV

Routes of administration: eIV = **extended intravenous**; IV = **short-term** intravenous.

^a Switching from a single subject cohort to a multiple-subject cohort will occur with cohort 3 or sooner if specific safety criteria are observed as described in Section [6.2.1.1.1](#).

^b If a dose reduction is needed according to instructions provided in [Table 6-3](#), treatment will be continued at a dose of 2.5 µg as specified in Section [6.2.2.3.5](#).

Note: The “b” cohort numbers are used to differentiate cohorts 1 through 10 denoted in previous versions of the protocol.

6.2.1.1.1 Single-subject Cohorts

The starting dose will be based on the MABEL (Saber, Del Valle, Ricks, & Leighton, 2017). Dose exploration will begin with single-subject cohort(s). The starting dose is expected to have the first dose C_{max} below the MABEL. Serum concentrations to be achieved with first 3 to 4 dose level cohorts are expected to be lower than those at which pharmacodynamic activity translating into treatment-related adverse events or efficacy is predicted to be observed. Therefore, the first 2 cohorts are pre-planned single subject cohorts.

If a subject in the first single-subject cohort does not experience a grade 2 or higher adverse event at least possibly related to AMG 910 or DLT (Section 6.2.1.3) during the initial 28 days of treatment (DLT window for single-subject cohorts), then the next subject may be dosed at the next higher dose level(s) per [Table 6-2](#).

In consequence, switching from a single subject cohort to a multiple-subject cohort will occur with cohort 3 or sooner if any of the following safety criteria are observed during the DLT window:

- DLT (Section 6.2.1.3), or
- Grade ≥ 2 adverse events based on CTCAE version 5.0, at least possibly related to AMG 910, with the exception of lymphopenia or lymphocyte count decreased.

NOTE: See [Table 6-3](#) for CRS and TLS grading criteria.

The DLRT will convene to review the safety data and recommend the appropriate dose to be implemented. The recommended dose will not exceed the levels recommended by the BLRM in the dose escalation portion and the next pre-defined dose level listed in [Table 6-2](#). The DLRT may also convene ad hoc meetings any time to review safety data if deemed necessary.

Determination of whether a subject is evaluable for DLT assessment will be made by DLRT in accordance with the following rules:

- Subjects who receive study treatment (at least 80% of the planned dose for cycle 1) and remain on study through the DLT assessment window will be considered DLT-evaluable.
- Subjects who discontinue from the study prior to completing the DLT assessment window for reasons other than a DLT will be considered non-evaluable for dose-escalation decisions and MTD determination and may be replaced by an additional subject at that same dose level.

- Subjects who discontinue from the study prior to completing the DLT assessment window for reasons other than a DLT will be considered non-evaluable for dose-escalation decisions and MTD determination and may be replaced by an additional subject at that same dose level.

Dose Level Determination

A recommendation to escalate to a higher dose level will only occur when the previous dose level has been found to be reasonably tolerated based on available study data and upon unanimous agreement of the DLRT members. Available data from previous cohorts will also be considered. Dose level recommendations will be made on a treatment cohort basis (not on an individual basis). After receiving the DLRT recommendation, Amgen will issue a written notification of the dose change decision to investigators. Further information on dose level review meetings is provided in Appendix 3 (Section 11.3).

Dose Cohort Stopping Rules

Dose escalation will follow the pre-defined dose levels in [Table 6-2](#) until a subject experiences a DLT. Then the dose for the subsequent cohorts will be decided by the DLRT after evaluating all available safety, laboratory, and PK data as well as the recommendation from the BLRM. Dose escalation/de-escalation decisions in multiple-subject cohorts will be guided by the BLRM model of dose toxicity. The MTD for BLRM is the dose level predicted to have the highest probability of a DLT rate within the target interval of 20% to 33%, subject to overdose control. To control the risk of overdose, the MTD must have less than a 40% predicted probability of overdosing (DLT rate > 33%).

If late onset adverse events (ie, after the 28-day DLT period) occur or late findings from endoscopic evaluations are reported during a cohort, the DLRT may adaptively re-consider the doses evaluated within a cohort for subsequent dosing and/or possibly trigger a de-escalation or withholding of additional doses in subsequent cohorts. Based on the BLRM model and after reviewing all available safety and tolerability data, the DLRT may recommend dosing at intermediate dose levels between the planned dose levels in [Table 6-2](#).

The Amgen Medical Monitor may suspend dosing and convene a dose level review meeting (DLRM) at any time based on emerging safety data.

Dose escalations will end once any of the following events occur:

- Highest planned dose level is determined to be safe and tolerable (minimum of 6 treated subjects on this dose level).
- The MTD is identified. A dose level is considered the MTD when the BLRM recommends treatment at this dose level and 6 or more evaluable subjects have already been treated at this dose level.

- On the basis of a review of real-time safety data and available preliminary PK data, dose escalation may be halted or modified by the Sponsor as deemed appropriate. A re-evaluation of the risk/benefit for the study will be necessary after the following observations:
 - Gastrointestinal events of CTCAE grade 3 in 2 subjects, with the exemption of nausea, vomiting, and abdominal pain, and gastrointestinal events of CTCAE grade 4 in 2 subjects if events are at least possibly related to AMG 910
 - Gastrointestinal event of CTCAE grade 5 in 1 subject, at least possibly related to AMG 910

To acquire additional safety and pharmacodynamic data to better inform the RP2D, additional subjects may be enrolled at a dose level that has been shown to not exceed the MTD based on the dose-escalation criteria described above, and at which there is evidence of anti-tumor activity and/or pharmacodynamic biomarker modulation. Up to approximately 3 additional subjects per dose level may be enrolled.

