3	Interrupt	
 Tube feed/TPN Other medical interventions as clinically indicated and per institutional guidelines Reoccurrence of event: Same management and GI consult 	
 Resolved or improved to grade \leq 1 in 48 hours 
 Dose Modification: Resume at same dose Re-start with next scheduled infusion do not resume prior infusion or administer delayed infusion. For elV infusion administration: In case the interruption does not exceed 24 hours, the infusion can be restarted at the same dose without additional measures. If the interruption exceeds 24 hours, the restart of the infusion should be performed under the supervision of the investigator or designee and premedication as described in Section 6.1.4 should be administered. If the interruption exceeds 48 hours, treatment initiation with elV infusion should be restarted following the dosing schedule and SoA for cycle 1 starting with day 1. Restarting due to any elV infusion interruption should be discussed with the medical monitor. Refer to Section 6.2.3. Second event occurrence: Resolved or improved to grade \leq 1 in 48 hours 
 Dose Modification: Consider next lower dose at investigator's discretion Subsequent event occurrence: Re-start possible after discussion with Amgen Medical Monitor 
 Dose Modification: Per discussion with Amgen Medical Monitor Second event that requires TPN or feeding tube can only be re-started following discussion with the Amgen Medical Monitor 	If not returned to grade \leq 1 in 48 hours after interruption
4	Interrupt	
 Hospitalization for tube feeding/ TPN Other medical interventions as clinically indicated and per institutional guidelines GI consult 	
 Re-start possible at next lower dose if resolved or improved to grade \leq 1 in 72 hours following discussion with GI consult and Amgen Medical Monitor Re-start with next scheduled infusion, do not resume prior infusion or administer delayed infusion Second event that require TPN or feeding tube can only be re-started following discussion with the Amgen Medical Monitor 	If not returned to grade \leq 1 in 72 hours after interruption OR After second occurrence of a grade 4 event after restart of investigational product

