9.4.1 Planned Analyses

9.4.1.1 Interim Analysis and Early Stopping Guidelines

Safety data will be reviewed on an ongoing basis. Based on accumulating toxicity information, BLRM will be used to make dosing recommendations. In DLRMs, Amgen,

in consultation with the site investigators, will review the BLRM recommended dose level and will review all available cumulative data by cohort prior to making dose escalation recommendations. As a sensitivity analysis, a 1-parameter Continual Reassessment Method model may be used to estimate the dose-toxicity relationship and to estimate the dose level closest to a 25% DLT rate in order to help make dose escalation decisions. Adverse events and DLTs observed in all subjects will be evaluated continually and fully integrated into all DLRCMs and considered in all enrollment and dosing decisions.

During dose expansion, futility will be assessed after treating 15 and 25 subjects for at least 8 weeks of treatment. If the observed rate of responses is consistent with a lower than 15% response rate, enrollment may be terminated due to futility. As appropriate, enrollment to dose expansion may continue during the period of first 8 weeks follow up for response. For purposes of assessing futility, a response is defined as an objective response per RECIST 1.1. The guidelines for early termination due to futility are as follows:

Number of Treated Subjects	Futility Termination Guideline
15	1 or fewer responders
25	4 or fewer responders
36	Enrollment to dose expansion complete

If the true response rate is 15% then these termination guidelines result in a 69.4% probability of terminating dose expansion early with an expected sample size of 25 subjects. If the true response rate is 30% then there is a 90% probability of continuing enrollment to n = 36 total subjects.

During dose expansion, Amgen will conduct evaluations of the ongoing grade 4 or higher treatment-related adverse event rate to assess if the threshold for possible early trial termination has been reached. If this threshold is met, enrollment to dose expansion will be halted pending review of safety data by the DLRT. After receiving the DLRT recommendation, Amgen will choose to take 1 of the following actions.

- 1) Terminate the trial
- 2) Amend the protocol to potentially improve the benefit/risk for subjects (eg, increase safety monitoring, modify dose/schedule, mandate premedication)
- 3) Continue dose expansion without any changes

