11.3 Appendix 3. Study Governance Considerations

Dose Level Review Team

A DLRM is conducted to review and interpret safety data for the purposes of making recommendations about dose-level escalation (either to the next planned dose or to an intermediate dose), dose level de-escalation, cohort continuation, or cohort expansion; making recommendations about non-dose escalation cohorts (eg, expanded, highest dose and/or final cohort); and evaluating safety signals for purposes of applying Dose Cohort Stopping Rules. The required Dose Level Review Team (DLRT) members are the Amgen Medical Monitor, Global Safety Officer (GSO), and Site Investigators. The DLRT will include only actively screening and enrolling Site Investigators. The Amgen Medical Monitor, GSO, and Site Investigators are the only voting DLRT members. The following non-voting Amgen representatives may also be part of the DLRT: clinical study manager, biostatistician, and/or PK scientist.

The Amgen Medical Monitor must be in attendance and cannot be represented by a voting designee or delegate. Voting designees can be identified as appropriate by the GSO or Site Investigator(s). A Site Investigator may identify a delegate (eg, sub-Investigator) who is listed in the Delegation of Authority. If a Site Investigator does this, the Site Investigator must provide written agreement with the designee or delegate's vote.

For a DLRM to occur, the Amgen Medical Monitor must attend, and the GSO or delegate must attend. In addition, a quorum of Site Investigators must be present. A quorum is defined as more than 50% of the participating investigators or their qualified designee. The DLRM will be rescheduled if these requirements are not met.

All available study data, including demographics, investigational product administration, medical history, concomitant medications, adverse events, ECG, vital signs, and laboratory results will be reviewed. Data to be reviewed will be queried.

DLRM voting will occur as follows: there will be a total of 3 votes, 1 for the Amgen Medical Monitor, 1 for the GSO or delegate, and 1 for all of the Site Investigators or delegates combined. Regardless of how many Site Investigators there are, all of the Site Investigators combined will have a total of 1 vote decided by a majority of the investigators (defined as greater than or equal to 50%).

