DLRM recommendations to escalate to the next planned cohort, or to an intermediate cohort, must be by unanimous vote. If the voting members of the DLRT are not able to reach a unanimous recommendation on whether to escalate to the next planned cohort

or to an intermediate cohort, then this should be reflected in the DLRM Memo. Other recommendations, such as expanding a cohort or lowering a dose will be made by a majority vote.

Regulatory and Ethical Considerations

This study will be conducted in accordance with the protocol and with:

- Consensus ethical principles derived from international guidelines including the Declaration of Helsinki and Council for International Organizations of Medical Sciences International Ethical Guidelines
- Applicable International Conference on Harmonisation (ICH) Good Clinical Practice (GCP) Guidelines
- Applicable ICH laws and regulations

The protocol, protocol amendments, informed consent form, Investigator's Brochure, and other relevant documents (eg, subject recruitment advertisements) must be submitted to an Institutional Review Board (IRB)/Independent Ethics Committee (IEC) by the investigator and reviewed and approved by the IRB/IEC. A copy of the written approval of the protocol and informed consent form must be received by Amgen before recruitment of subjects into the study and shipment of Amgen investigational product. Amgen may amend the protocol at any time. The investigator must submit and, where necessary, obtain approval from the IRB/IEC for all subsequent protocol amendments and changes to the informed consent document. The investigator must send a copy of the approval letter from the IRB/IEC and amended protocol Investigator's Signature page to Amgen prior to implementation of the protocol amendment at their site.

The investigator will be responsible for the following:

- Providing written summaries of the status of the study to the IRB/IEC annually or more frequently in accordance with the requirements, policies, and procedures established by the IRB/IEC
- Obtaining annual IRB/IEC approval/renewal throughout the duration of the study. Copies of the investigator's reports and the IRB/IEC continuance of approval must be sent to Amgen
- Notifying the IRB/IEC of serious adverse events occurring at the site, deviations from the protocol or other adverse event reports received from Amgen, in accordance with local procedures

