Examples of such events include invasive or malignant cancers, intensive treatment in an emergency room or at home for allergic bronchospasm, blood dyscrasias or convulsions that do not result in hospitalization, or development of drug dependency or drug abuse.

Recording Adverse Events and Serious Adverse Events

Adverse Event and Serious Adverse Event Recording

- When an adverse event or serious adverse event occurs, it is the responsibility of the investigator to review all documentation (eg, hospital progress notes, laboratory, and diagnostics reports) related to the event.
- The investigator will then record all relevant adverse event/serious adverse event information in the Events case report form (CRF).
- The investigator must assign the following adverse event attributes:
 - Adverse event diagnosis or syndrome(s), if known (if not known, signs or symptoms);
 - Dates of onset and resolution (if resolved);
 - Did the event start prior to first dose of investigational product, other protocol-required therapies;**
 - Assessment of seriousness;**
 - Severity (or toxicity defined below);
 - Assessment of relatedness to investigational product (AMG 910), other protocol-required therapies, and/or study-mandated activity **and/or procedures;**
 - Action taken; **and**
 - Outcome of event.**
- If the severity of an adverse event changes from the date of onset to the date of resolution, record a single event for each level of severity on the Events CRF.
- It is not acceptable for the investigator to send photocopies of the subject's medical records to sponsor in lieu of completion of the Events CRF page.
- If specifically requested, the investigator may need to provide additional follow-up information, such as discharge summaries, medical records, or extracts from the medical records. In this case, all subject identifiers, with the exception of the subject number, will be blinded on the copies of the medical records before submission to Amgen.

- The investigator will attempt to establish a diagnosis of the event based on signs, symptoms, and/or other clinical information. In such cases, the diagnosis (not the individual signs/symptoms) will be documented as the adverse event/serious adverse event.

Evaluating Adverse Events and Serious Adverse Events

Assessment of Severity

The investigator will make an assessment of severity for each adverse event and serious adverse event reported during the study. The assessment of severity will be based on:

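### The first gastrointestinal trigger for re-evaluating the study misses one grade 3 plus one grade 4 subject counted at worst grade, and its joining word leaves two grade 4 subjects open to dispute

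*Protocol*

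**What the plan says.** Under Dose Cohort Stopping Rules in Protocol Section 6.2.1.1.2, the plan states: "A re-evaluation of the risk/benefit for the study will be necessary after the following observations". Two observations follow.

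- The first is "Gastrointestinal events of CTCAE grade 3 in 2 subjects, with the exemption of nausea, vomiting, and abdominal pain, and gastrointestinal events of CTCAE grade 4". The grade 4 half, like the grade 3 half, needs 2 subjects, and the events must be at least possibly related to AMG 910.
- The second is one related grade 5 GI event. It is clear and is not questioned here.

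Four other places bear on how the first bullet works.

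- **Section 6.2.1.3** writes the DLT criterion for non-hematologic events as grade 3 or above, so the protocol uses an *or higher* form when it means one.
- **Appendix 4 (Section 11.4)** tells the investigator, when severity changes, to "record a single event for each level of severity on the Events CRF". A grade 4 subject may therefore also carry a grade 3 record.
- **Table 6-3** has a separate row for grade 4 vomiting, with permanent discontinuation "After second occurrence of a grade 4 event after restart of investigational product". The GI bullet, however, exempts vomiting at grade 3.
- **Section 9.4.1.1**, in the dose-expansion stopping text, separately requires the study's risk/benefit to be re-evaluated if the same grade 4 stomach toxicity is seen in 2 or more subjects.

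The SAP does not restate the GI trigger.

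**The concern.** A safety trigger should not fire for a milder pattern and stay silent for a worse one. The first bullet can do so, because it sets a separate count for each exact grade and never pools the two grades. It also does not say whether its halves are alternatives, or whether a subject counts at worst grade or at every recorded grade. Two careful readers could apply it differently to the same data.

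What can be missed is the mandatory study-level re-evaluation. The Protocol names stomach and duodenum as target organs of toxicity (Section 2.3.3), so this trigger guards an expected toxicity in a first-in-human trial.

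**Working it through.** The plan states no operating characteristic for this trigger, so there is no figure to reproduce. The check is one of logic, followed by an illustration.

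**Step 1. Patterns.** Let *a* be the number of subjects whose worst related, non-exempt GI event is grade 3, and *b* the number whose worst is grade 4. The rules are:

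- literal: *a* ≥ 2 and *b* ≥ 2
- alternatives: *a* ≥ 2 or *b* ≥ 2
- pooled (the fix): *a* + *b* ≥ 2

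| (a, b) | Literal | Alternatives | Pooled |
|---|---|---|---|
| (2, 0) | no | yes | yes |
| (1, 1) | no | no | yes |
| (0, 2) | no | yes | yes |
| (1, 2) | no | yes | yes |
| (2, 1) | no | yes | yes |
| (2, 2) | yes | yes | yes |

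The (1, 1) gap comes from the exact grades, so changing *and* to *or* does not close it. The (0, 2) gap exists only on the literal reading.

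**Step 2. Effect of the recording rule.** If every recorded grade counts, a grade 4 subject with a non-exempt grade 3 record adds to both counts. Pattern (1, 1) then has two grade 3 subjects and triggers on the alternatives reading. Pattern (0, 2) triggers even on the literal reading if both subjects have such a record. Grade 4 vomiting cannot supply the record, because grade 3 vomiting is exempt. So one grade 3 gastritis plus one grade 4 vomiting, each the subject's only relevant event, triggers nothing under either counting method.

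**Step 3. Illustrative size, late events only.** Most related grade 3 or higher GI events inside the DLT window are DLTs, so the illustration covers events after it. The documents give no late-event rates. The following are assumptions:

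- per-subject worst-grade rates p3 = p4 = 1% or 2%, the same at all doses
- N = 12, 24 or 34 subjects; 34 is the dose-exploration maximum in Section 6.2.1.1
- q, the share of grade 4 subjects with a counted non-exempt grade 3 record, set to 0, 0.5 or 1

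On the alternatives reading only (1, 1) is missed:

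P(missed) = N(N−1) × p3 × p4 × (1−p3−p4)^(N−2) × (1−q)

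For N = 34 at 2%/2% and q = 0: 34 × 33 × 0.02 × 0.02 × 0.96^32 = 0.4488 × 0.2708 = 12.2%.
For N = 12 at 1%/1% and q = 0: 12 × 11 × 0.01 × 0.01 × 0.98^10 = 0.0132 × 0.8171 = 1.1%.

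The literal column sums multinomial probabilities over *b* ≥ 2 with fewer than two counted grade 3 subjects. It takes no account of the Section 9.4.1.1 stomach rule, so it overstates the gap wherever that rule applies.

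| Rates | N | Alternatives: 2 or more subjects at grade 3–4, no trigger (q = 0 / 0.5 / 1) | Literal: 2 or more grade 4 subjects, no trigger (q = 0 / 0.5 / 1) |
|---|---|---|---|
| 1%/1% | 12 | 1.1 / 0.5 / 0% | 0.6 / 0.4 / 0% |
| 1%/1% | 24 | 3.5 / 1.8 / 0% | 2.3 / 1.5 / 0% |
| 1%/1% | 34 | 5.9 / 2.9 / 0% | 4.4 / 2.6 / 0% |
| 2%/2% | 12 | 3.5 / 1.8 / 0% | 2.3 / 1.5 / 0% |
| 2%/2% | 24 | 9.0 / 4.5 / 0% | 7.7 / 4.3 / 0% |
| 2%/2% | 34 | 12.2 / 6.1 / 0% | 12.8 / 6.4 / 0% |

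**The case against.** **The alternatives reading is the natural one.** The bullet sits in a list of observations. Requiring two grade 3 and two grade 4 subjects together would mean that two life-threatening GI events alone prompt nothing. Section 9.4.1.1 treats two grade 4 stomach events as enough by themselves, which points the same way. This stands. A reader might infer that the sponsor meant to ignore two grade 4 subjects, and the documents do not support that.

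**Section 9.4.1.1 already covers two grade 4 subjects.** Partly. It needs the same toxicity, is limited to the stomach, and sits in the dose-expansion text. Different toxicities, non-stomach GI events and the one-plus-one pattern remain outside it.

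**Separate thresholds per grade are a legitimate choice.** They are. If that is the choice, the rule should still say that the halves are alternatives and how a subject is counted.

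**Other safeguards apply.** A reader might infer that such events could escape review altogether. They do not.

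- Within the DLT window, related grade 3 gastritis and related grade 4 vomiting are both DLTs under Section 6.2.1.3 and feed the dose-toxicity model.
- Grade 3 or 4 gastritis, gastric hemorrhage or gastric perforation ends that subject's treatment (Table 6-3).
- Section 6.2.1.1.2 says: "A recommendation to escalate to a higher dose level will only occur when the previous dose level has been found to be reasonably tolerated". Appendix 3 (Section 11.3) adds: "DLRM recommendations to escalate to the next planned cohort, or to an intermediate cohort, must be by unanimous vote".
- Section 9.4.1.1 says that DLTs and other safety events "observed in all subjects will be evaluated continually and fully integrated into all DLRCMs and considered in all enrollment and dosing decisions". Appendix 3 says of dose level review: "All available study data, including demographics, investigational product administration, medical history, concomitant medications, adverse events, ECG, vital signs, and laboratory results will be reviewed".
- The sponsor may halt or modify escalation, and the Medical Monitor may suspend dosing.

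These safeguards are dose-level, subject-level or discretionary, and do not replace the mandatory study-level re-evaluation. They do keep the point small.

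**Conclusion.** The concern holds as a minor drafting defect in a stated safety rule. With worst-grade counting, one related grade 3 plus one related grade 4 GI subject misses the mandatory re-evaluation on both readings. On the likely intended reading, two grade 3 gastritis subjects would trigger it. This follows from the text alone and needs no assumed rate.

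The two-grade-4 gap is weaker. It needs the literal reading, which is the less likely one, and Section 9.4.1.1 narrows it wherever that rule applies.

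The probabilities only illustrate. They rest on assumed rates and an assumed q, and they fall to 0% if every grade 4 subject also has a counted grade 3 record. They should not be read as evidence that the gap is likely to matter in this trial. SAP Section 7.1 records early termination, so the gain lies in the rule as written or reused.

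**What to change.** Replace the two bullets with wording such as: *gastrointestinal events of grade 3 or higher, at least possibly related to AMG 910 (excluding grade 3 nausea, vomiting and abdominal pain), in at least 2 subjects, each counted once at worst grade; or a related grade 5 gastrointestinal event in 1 subject.*

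If the sponsor prefers separate thresholds per grade, the minimum is to change *and* to *or*, write *at least 2 subjects*, and state the counting rule. That leaves the one-plus-one pattern untriggered by open choice.

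The change is to protocol wording only. Over the assumed ranges, the pooled wording raises the chance of a trigger by 0 to 12 percentage points against the alternatives reading (for example 27.5% to 39.7% at N = 34, 2%/2%, q = 0). Against the literal reading it adds about 2 to 38 points (2.0% to 39.7% in the same case). The consequence of a trigger is possibly one more risk/benefit review, not a stop.
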